### Schedule of Assessments (cont.)

- l Only assessed in patients aged 9–17 years at Visit 1 and annually thereafter.
- m For a list of all safety laboratory assessments, please refer to Section 4.4.8.
- n For patients aged 6–17 years, *includes* thyroid hormones (free thyroxine T4 and thyroid-stimulating hormone); and for patients aged 12–17 years or younger who have menses, also includes estradiol, follicle-stimulating hormone, *and* luteinizing hormone. Hormone assessments should occur every 12 months.
- o Urine pregnancy tests will be performed at all visits. If a urine pregnancy test is positive, it must be confirmed by a serum pregnancy test.
- p Includes dipstick (pH, specific gravity, glucose, protein, ketones, blood). If deemed necessary for further investigation, the treating physician can request microscopic examination (sediment, RBCs, WBCs, casts, crystals, epithelial cells, bacteria). Urinalysis should occur every 12 months.
- q *Should be performed predose.*
- r Actual PK sampling times must be documented. Actual date and time of study drug administration for the preceding two doses (except on Visit 1) must be documented in the eCRF.
- s Separate whole blood samples for SMN protein and SMN2 mRNA assessment. Please refer to Section 4.4.8.1.
- t Serum sample for fluid biomarkers. Please refer to Section 4.4.8.1.2.
- u In case it was not possible to collect *the baseline* sample during Visit 1, a sample for clinical genotyping should be drawn at the next visit. Please refer to Section 4.4.8.2.
- v ECG should be performed at screening and Visit 2 and then yearly from start of treatment.
- w *If dose increase visit is performed at a scheduled visit, ECG does not need to be performed since a 24-hour Holter ECG monitoring is being performed.*
- x Please refer to Section 4.4.10 for age-specific assessment and details. Complete before all other assessments during the study visit.
- y Please refer to Section 4.4.11 for details on the Caregiver-Reported Outcomes.
- z After informed consent has been obtained but prior to initiation of study drug, only serious adverse events caused by a protocol-mandated intervention should be reported. After initiation of study drug, all adverse events will be reported until 28 days after the last dose of study drug. After this period, the Sponsor should be notified if the investigator becomes aware of any serious adverse event that is believed to be related to prior study drug treatment (see Section 5.6). The investigator should follow each adverse event until the event has resolved to baseline grade or better, the event is assessed as stable by the investigator, the patient is lost to follow-up, or the patient withdraws consent. Every effort should be made to follow all serious adverse events considered to be related to study drug or trial-related procedures until a final outcome can be reported.
- aa Telephone calls: After Visit 5, telephone calls should occur every 12 weeks ( $\pm$  7 days). Please refer to Section 4.4.18 and Appendix 3.
- bb Optional sample to be collected only for patients providing additional consent and not applicable for a site that has not been granted approval for RCR sampling. If the sampling for DNA specimens was missed during baseline, it may be collected in the next scheduled visit.
- cc *The digital biomarker smartphone will be handed to patients at the first visit after the amendment. The smartphone must be returned to the clinical site in case of study withdrawal, end of the study, or upon request.*

## Appendix 2

### Historical Data Collection

The following information will be collected at screening from patients who sign separate consent.	Screening visit of BN29854	Possible assessments during all routine clinical visits d
Informed consent for Historical Data collection	x	
Last study visit date in previous study	x	
Clinical visit dates		x
Motor Function Measure at each visit a		x
Patient disability status b		x
Medical procedures c		x
Therapies c		x
Participation in other investigational studies	x	

a Motor Function Measure using any SMA validated motor function scale, such as the MFM and HFMS.

b e.g., using Brooke or Vignos scales.

c Medical procedures and therapies that in the opinion of the investigator are related to the natural course of SMA disease.

d The site should request to the patient and/or treating physician all possible assessment that occurred between last visit in TRO19622CLEQ1275-1 or TRO19622CLEQ1115-1 and enrollment in BN29854. It is possible that all information listed was not acquired during routine clinical visits.

## **Appendix 3**

### **Telephone Interviews**

The following semi-structured telephone interview should occur after Visit 5, 12 weeks ( $\pm 7$  days) *after each study visit*. The purpose of this interview is to identify any new or worsening symptoms that warrant an unscheduled visit or reporting of an adverse event.

Please ask the following questions and record patient's answers during the Telephone Interview:

1. Since the last time we talked (at site or over the telephone), have you had any worsening medical problems? If yes, what were they?

---

---

2. Since your last visit or telephone interview, have you taken any new medicines? If yes, what were they?

---

---

3. Have you had problems or issues with the preparation or handling of the study drug?

---

---

If the patient answered YES to any question, contact the Treating Investigator and review the patient's answers. The Investigator can determine if an unscheduled visit is required.

Record any pertinent comments made by the patient during the interview:

---

---

NAME: \_\_\_\_\_ Date: \_\_\_\_\_

Name of person completing the telephone interview.

## **Appendix 4**

### **Formula for Calculation of Body Mass Index**

#### **Formula for Calculation of Body Mass Index (BMI)**

$$BMI = \frac{Weight\ (kg)}{[Height(m)]^2}$$

1. BACKGROUND

This analysis plan documents the statistical methods that will be used to summarize and analyze efficacy and safety data collected during the open-label treatment phase of study BN29854 from patients with spinal muscular atrophy (SMA). The main purpose of this document is to describe the data handling rules, derivation rules and statistical methods used for these analyses.

The planned analyses will also use observational data from untreated SMA patients to compare study findings with the natural history of the disease.

2. STUDY DESIGN

Study BN29854 is a phase II, multicenter, open-label, single arm study to evaluate the long-term safety, tolerability and effectiveness of olesoxime (Roche No. RO7090919) 10mg/kg q.d. in patients with SMA who previously participated in one of the following two studies:

- Open-label phase Ib, dose-ranged, single and multiple dose study to assess safety and pharmacokinetics of olesoxime in 6-25 year old SMA patients (Trophos No. TRO19622CLEQ1115-1, Roche No. WP29845), and
- Phase II multicenter, randomized, adaptive, double-blind, placebo controlled study to assess safety and efficacy of olesoxime in 3-25 year old Type 2 or non-ambulatory Type 3 SMA patients (Trophos No. TRO19622CLEQ1275-1, Roche No. WN29836).

The study will consist of historical data collection, screening, treatment and safety follow-up periods. Patient visits will occur at 13, 26, 39 and 52 weeks and every 26 weeks thereafter for medical examinations, as well as safety and efficacy assessments. In addition, patients and their treating physicians will be requested to provide data for the period between the patients' last visit in the previous Trophos study and the screening period of study BN29854. Enrollment in the open-label treatment phase of the study is independent from the historical data collection, and a separate Informed Consent Form is required for each part. Patients (or their legal representatives) who do not consent to the historical data collection are still eligible to participate in the treatment phase of the study, and vice versa. The analysis methods that will be used for the historical data will be reported in a separate statistical analysis plan (SAP).

The study will continue until olesoxime is commercially available in the patient's country, or as per local regulation, or per the Sponsor's decision to terminate the olesoxime program for SMA, but will not exceed four years after the last patient was enrolled in the study. In the UK the study will last for a fixed period of three years after the last patient was enrolled.

2.1 OUTCOME MEASURES

2.1.1 Primary Efficacy Outcome Measures

The primary efficacy outcome measure is the motor function measure (MFM) D1+D2 score.

2.1.2 Secondary Efficacy Outcome Measures

Secondary outcome measures include:

- MFM total score (D1+D2+D3)
- Pediatric Quality of Life Inventory (PedsQL) 4.0 Generic Core scale and PedsQL 3.0 Neuromuscular module
- Work productivity and activity impairment: caregiver (WPAI:CG)
- SMA related medical complications and procedures

2.1.3 Exploratory Efficacy Outcome Measures

Exploratory outcome measures include:

- Forced vital capacity (FVC)
- MFM D1+D2 responder rates, where a responder is defined as no worsening from baseline in the MFM D1+D2 score
- Hammersmith functional motor scale (HFMS) [before removal from schedule of assessments as of protocol version 3]

2.1.4 Pharmacokinetic Outcome Measures

The pharmacokinetic outcome measure for this study is the predose (trough) plasma olesoxime concentration.

2.1.5 Safety Outcome Measures

Safety outcome measures include:

- Adverse events (AEs)
- Laboratory tests
- Vital signs
- Electrocardiogram (ECG)

2.2 DETERMINATION OF SAMPLE SIZE

The sample size will be determined by the number of patients who participated in study TRO19622CLEQ1115-1 or TRO19622CLEQ1275-1 (170 in total) who meet the enrollment criteria and who consent to participate in the treatment phase of study BN29854.

2.3 ANALYSIS TIMING

The final analysis will be performed on all data collected up to the end of the study, after the last patient has completed the last follow-up visit.

Interim analyses of the data may be performed prior to final database lock to adapt to information that may emerge during the course of the study or for submissions to health authorities.

3. STUDY CONDUCT

3.1 RANDOMIZATION

BN29854 is a single arm, open-label study, and all patients receive olesoxime at 10mg/kg q.d.

3.2 DATA MONITORING

Due to the open-label design of this study it is not deemed necessary to have an independent Data Monitoring Committee (iDMC).

4. STATISTICAL METHODS

4.1 ANALYSIS POPULATIONS

4.1.1 Intent-to-Treat Population

The intent-to-treat (ITT) population will include all patients who received at least one dose of study medication and have at least one post-baseline assessment of MFM. The ITT population will be the primary population for efficacy analyses.

4.1.2 Safety Population

The safety population will include all patients who received at least one dose of study medication. All safety analyses will be based on the safety population.

4.1.3 Historical Comparison Population

The historical comparison population will consist of SMA patients selected from natural history databases containing MFM data. This population will be used to select matches for patients in the ITT population in order to compare data collected during the study with natural history data describing motor function.

The historical comparison population will be chosen to match the ITT population as closely as possible with respect to age and SMA type. This population will include patients with Type 2 or Type 3 SMA (non-ambulatory) who have a confirmed diagnosis of SMA and at least two MFM measurements. The age range in this population will be restricted to a similar age range to that observed in the ITT population, with a minimum age of 6 years old or the minimum age in the ITT population minus 2 years (whichever is greater), up to the maximum age in the ITT population plus 5 years. Only patients with at least two MFM-32 assessments performed when the patient is non-ambulant and ≥ 6 years old will be considered for inclusion in the historical comparison population.

One patient will be selected from the natural history databases to match the patient from study TRO19622CLEQ1115-1 with Type 1 SMA. Gender will be matched exactly and

age will be matched within a window of 2 years. If there is more than one untreated patient meeting these criteria, one patient will be selected for inclusion in the historical comparison population using the following hierarchy:

1. The patient with the closest age,
2. The patient with the closest MFM D1+D2 score at baseline,
3. The patient with the closest baseline MFM assessment date,
4. A patient will be selected randomly.

The following data sources will be used to select patients for the historical comparison population:

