4.1.4 Matched Patient Population

In order to account for differences between patients in the ITT population (treated) and those in the historical comparison population (untreated), several matching methods for

balancing baseline covariates will be considered depending on sample size, data availability and data quality.

If there is sufficient data, each individual in the ITT population will be matched to an individual in the historical comparison population (one-to-one matching) with respect to age, gender, SMA type and baseline MFM D1+D2 score. Gender and SMA type will be matched exactly, followed by optimal Mahalanobis distance matching within these groups for the age and baseline MFM D1+D2 score. In order to determine the 'closeness' between individuals to use in matching, we define the Mahalanobis distance, D_{ij} , between the i^{th} treated unit and j^{th} potential untreated unit:

$$D_{ij} = (x_i - x_j)^T \Sigma^{-1} (x_i - x_j)$$

where x_i and x_j are the observed values of the matching variables (age and baseline MFM D1+D2 score) for treated unit i and untreated unit j , respectively, and Σ is the variance covariance matrix of X in the untreated group. Optimal matching will be used to minimize the total distance $T = \sum D_{ij}$.

Patients in the ITT population who erroneously perform the MFM-20 assessment at the baseline visit will not be included in the matched patient population. MFM-20 assessments performed at any post-baseline visit will be set to missing.

If one-to-one matching does not produce enough matches (if > 10% of the ITT population is not matched), optimal full matching will be performed, where one untreated unit may be matched to more than one treated unit, but each treated unit will only be matched to one untreated unit. The maximum number of times each untreated unit is matched with a treated unit will be equal to the smallest integer value greater than or equal to the maximum ratio of treated to untreated units in each combination of gender and SMA type (Type 2 male, Type 2 female, Type 3 male and Type 3 female). The number of times each untreated unit is matched will be monitored to ensure that the treatment effect estimate is not based on only a small number of untreated units.

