4.4 EFFICACY ANALYSIS

As this is a single arm, open-label study no formal hypothesis testing will be performed. Data collected during the treatment phase of this study will be summarized using descriptive statistics and will be compared with observational data describing the natural history of the disease.

The baseline value will be defined as the last non-missing value recorded prior to or on the first day of the study drug (Study Day 1).

Post-baseline efficacy assessments (scheduled every 26 weeks), including assessments performed at an early discontinuation visit, will be assigned to a scheduled study visit based on the following time windows:

Visit	Study Day	Time Window (in Study Days)
V3 (Week 26)	183	Day 2 – Day 274
V5 (Week 52)	365	Day 275 – Day 456
V6 (Week 78)	547	Day 457 – Day 638
V7 (Week 104)	729	Day 639 – Day 820
V8 (Week 130)	911	Day 821 – Day 1002
V9 (Week 156)	1093	Day 1003 – Day 1184
V10 (Week 182)	1275	Day 1185 – Day 1366
V11 (Week 208)	1457	Day 1367 – Day 1548
...		

If multiple valid values for a variable are recorded in the same time window, the record closest to the scheduled study visit will be selected for summary of the data.

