Descriptive statistics for the actual values and change from baseline values in the MFM D1+D2 score will be presented. The results will be presented according to the timings of the MFM assessment visits in the ITT population: 26, 52, 78, 104 and every 26 weeks thereafter after baseline until the end of the study. As the MFM measurements in the natural history databases were not all collected at specific time points after baseline measurements, the measurements will be assigned to a scheduled study visit based on the time windows defined above. If more than one MFM measurement is recorded in the same time window the assessment closest to the target visit day will be used. Mean changes in the MFM D1+D2 score and corresponding 95% CIs over time will also be presented graphically.

Given sufficient data, the change from baseline in the MFM D1+D2 score at weeks 26, 52, 78 and 104 will also be analyzed using a mixed-effects model for repeated measures (MMRM). The model will include the treatment group, age, gender, SMA type, visit, treatment-by-visit interaction, and the baseline MFM D1+D2 score as covariates. Matched set will be included in the model as a random effect.

An unstructured variance-covariance matrix will be applied to model the within-patient errors. The restricted maximum likelihood method will be used for estimates of variance components. Denominator degrees of freedom will be estimated using the Kenward-Roger approximation. A treatment-by-time interaction contrast will be constructed to estimate the difference between the two groups in the mean change from baseline at each visit, and the 95% CI for the treatment difference will be reported.

If there are a sufficient number of patients in the historical comparison population for one-to-one matching to be performed, but the covariate balance between the treated and untreated groups after matching is worse than the balance before matching, then the optimal full matching described in Section 4.1.4 will be performed, and the covariate balance in this new population will be assessed. If the covariate balance between the treated and untreated groups after optimal full matching is worse than the balance before matching (and worse than the balance after one-to-one matching, if applicable), descriptive statistics for the MFM D1+D2 score will be presented for the historical comparison population, and the treatment effect in the pooled ITT and historical

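### Natural-history controls qualify on any two MFM-32 assessments, so some matched controls may give the Week 26 to 104 model no value, or a lone near-baseline repeat counted as Week 26

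*SAP*

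**What the plan says.** SAP 4.1.3 (Historical Comparison Population) gives the entry rule for controls: "Only patients with at least two MFM-32 assessments performed when the patient is non-ambulant and ≥ 6 years old will be considered for inclusion". It states no minimum or maximum gap between the two assessments. The only indirect limit is the age range, which runs "up to the maximum age in the ITT population plus 5 years".

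SAP 4.1.4 matches controls to ITT patients "with respect to age, gender, SMA type and baseline MFM D1+D2 score". Length and timing of follow-up play no part. Optimal full matching replaces one-to-one matching if more than 10% of the ITT population is unmatched.

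SAP 4.4.1.2 recognises the timing problem: "As the MFM measurements in the natural history databases were not all collected at specific time points after baseline measurements", so "the measurements will be assigned to a scheduled study visit based on the time windows defined above". In the SAP 4.4 table the Week 26 window opens at Day 2 and closes at Day 274, and the Week 104 window is "Day 639 – Day 820". There is a tie-break: "If more than one MFM measurement is recorded in the same time window the assessment closest to the target visit day will be used".

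Given sufficient data, "the change from baseline in the MFM D1+D2 score at weeks 26, 52, 78 and 104 will also be analyzed" with a mixed model for repeated measures. Missing MFM scores are not imputed (SAP 4.4.1.1). Descriptive tables continue every 26 weeks to the end of the study. Baseline is defined by the first day of study drug (SAP 4.4), and no equivalent rule says which assessment is baseline for an untreated control with three or more.

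**The concern.** The entry rule asks whether a control has a second assessment, but not whether that assessment falls where the analysis can use it. Two things can then happen.

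- **No modelled outcome.** A control whose next MFM is after Day 820 is eligible and can be matched. It counts as a match for the 10% trigger and enters the balance check. It contributes nothing to the Week 26 to 104 model, while its treated partner stays in. The balance table then describes a sample that differs from the one modelled, and a control with in-window data may have been passed over.
- **Near-baseline repeat.** A control whose only MFM in the Week 26 window is a repeat before Day 92 has that value analysed as the Week 26 change. In a declining disease this makes the control decline look too small.

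Both fall mainly on the control side. Trial patients have scheduled MFM visits, with windows of 7 days either way up to Week 52 and 14 days after that (Protocol Appendix 1). The comparison with natural history is a secondary objective (Protocol 2.2).

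**Working it through.** **1. Reproduce the windows in SAP 4.4.** Target day = 7 × week + 1. Week 26 gives 183 and Week 104 gives 729. Cut points lie halfway between targets, for example (183 + 365)/2 = 274 and (729 + 911)/2 = 820. With the first window opened at Day 2, this reproduces all eight listed windows.

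**2. Compare their shape.** Week 26 reaches 183 − 2 = 181 days below target and 274 − 183 = 91 above. Every later listed window reaches 90 below and 91 above. A symmetric lower limit for Week 26 is 183 − 91 = Day 92.

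**3. Place a control with exactly two assessments, the first being Day 1.**

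| Day of second MFM | Window | In the model? |
|---|---|---|
| 2, 8, 15 or 31 | Week 26 | yes |
| 365 | Week 52 | yes |
| 820 | Week 104 | yes |
| 821 | Week 130 | no |
| 1096 | Week 156 | no |

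**4. See which sources can produce a late-only control.** Day 820 is 819 days after Day 1, or 819/30.4375 = 26.9 months. Planned follow-up is 12 months in ULENAP (SAP 4.1.3.1) and 12 to 24 months in NatHis-SMA (SAP 4.1.3.2), both inside that limit. The late-only case therefore arises mainly in the routine-care part of the MFM Database, collected since 2002.

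**5. Precision.** Let f be the share of one-to-one matched controls with no in-window outcome. With equal variances, and ignoring the matched-set correlation, the standard error of the treatment difference is multiplied by √[(1 + 1/(1 − f))/2]. The values of f are assumptions.

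- f = 10%: 1.027, about 3%
- f = 20%: 1.061, about 6%
- f = 30%: 1.102, about 10%

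**6. Week 26 bias.** Protocol 3.3.1 gives a placebo slope of −1.05 units per year. Expected decline is 1.05 × 183/365 = 0.53 at Day 183 and 1.05 × 30/365 = 0.09 at Day 30, a gap of 0.44. If a share g (assumed) of Week 26 control values come from about Day 30, mean control decline is understated by g × 0.44.

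- g = 10%: 0.04 units (8% of 0.53)
- g = 20%: 0.09 units (17%)
- g = 30%: 0.13 units (25%)

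The percentages equal g × (1 − 30/183), so they hold for any linear slope.

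**The case against.** The strongest reply is that the effect is small, local and partly guarded against.

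- **The closest-to-target rule.** An early repeat is used only if nothing nearer Day 183 lies in the same window. This stands, and it limits the second case to controls with a lone early repeat in that window. It does not remove the case.
- **The sources.** A reader might infer that all the natural-history data have haphazard timing. The SAP says only that not all measurements were taken at set times, and two of its sources have planned follow-up inside Day 820.
- **The model.** A mixed model does not need complete pairs, and it adjusts for age, gender, SMA type and baseline score. A missing partner costs precision. It biases the estimate only if the missingness is informative, and nothing in the documents shows that. The mismatch between the sample balanced and the sample modelled remains.
- **Late controls are not useless.** They can appear in the descriptive tables from Week 130 on.
- **Size and direction.** A shift of 0.09 units is small beside the 2-point MFM D1+D2 increase that Protocol 3.3.1 treats as clinically meaningful. It works against olesoxime.
- **Context.** No formal hypothesis test is planned, the primary objective is safety, and the model is run only if data suffice. The ITT rule also asks for just one post-baseline MFM with no interval, although scheduled visits largely settle that for treated patients.

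These points lower the importance of the concern. None supplies the missing interval rule.

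**Conclusion.** The point holds as a gap in the control entry rule. Followed as written, the SAP can match controls that give the Week 26 to 104 model no value, and can analyse a lone repeat from before Day 92 as a Week 26 change. How often either happens cannot be determined from the documents.

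On the assumed shares, the cost is about 3 to 10% on the standard error of the difference for 10 to 30% of controls without an in-window outcome. It is about 0.09 units of understated control decline at Week 26 if 20% of values come from near Day 30. The first figure rests on one-to-one matching, equal variances and no matched-set correlation. The second rests on a linear decline at the placebo slope.

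A reader might infer that the comparison is tilted in favour of the drug. The documents do not support that: with a declining course, early repeats understate a benefit, and only at Week 26. Nor do they support a loss of precision as large as 1/√(1 − f), which is 5, 12 or 20% at the same shares. That applies to the control mean alone, whereas the SAP reports a difference.

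**What to change.** **SAP 4.1.3.** Require each control to have a baseline MFM-32 and at least one further MFM-32 at Day 92 to 820, counting baseline as Day 1, with the patient non-ambulant and at least 6 years old at both. Take as baseline the earliest assessment that meets this, chosen from dates only. This also settles the baseline for controls with three or more assessments.

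**SAP 4.4.1.2.** For the natural-history comparison, start the Week 26 window at Day 92 in both groups.

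**SAP 4.1.4 and 4.4.1.2.** Run the matching, the 10% trigger and the balance check with the filtered control pool. Keep every ITT patient who is otherwise eligible for matching: dropping treated patients for lack of a post-baseline value would condition on follow-up.

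**Cost.** This takes a few lines of SAP text and a date filter before matching, with no need to look at scores. The control pool becomes somewhat smaller. It loses controls with only a Day 2 to 91 repeat and controls followed only after Day 820, and the latter also drop out of the late descriptive tables. The Week 26 window for treated patients would differ slightly from the one in the single-arm summaries. A treated patient whose only early MFM is before Day 92, for example at early discontinuation, would have no Week 26 value in this comparison.
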